#### 5.4.2.1 Cox Proportional Hazard Model

Time-to-event (survival) analyses will be undertaken using Cox proportional hazard models (Cox model) to describe how the hazard increases for each unit increase of the regressor variables. Crude and adjusted hazard ratios (HR) comparing subpopulations under study will be calculated for all primary outcomes and 95% HR confidence limits (Wald) are provided. The crude model refers to a univariable model which includes exposure as the only explanatory factor. Potential predefined event-specific prognostic factors (section 5.4.2) are included in multiple models. In the Cox model, recurrent events are included.

18

 See Appendix III for all potential prognostic factors for each primary and secondary outcome.

Supporting document SOP BMT 01.09 – Doc 5002.02 – Effective date 21.03.2017

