A conservative estimate of the prevalence rate for depression in women with endometriosis is 20%. This figure is based on a systematic literature review of the available evidence and an analysis of EURAS/INAS results [10-12]. For newly diagnosed or worsening depression the expected incidence rate is at least 0.01. Based on this incidence, the sample size outlined below was calculated; in case the study shows other incidence rates at a later point in time, a re-calculation may be necessary and will be discussed with the Safety Monitoring and Advisory Council if required.

Based on the natural history of endometriosis treatment, we anticipate that the majority of women will stop or change treatment regimes during the course of this study. We expect an incidence rate of women ceasing or changing treatment ('treatment failure') for other endometriosis medications due to lack of efficacy, loss of efficacy or an adverse drug reaction of at least 0.3. For the DNG cohort a proportion of 0.25 of the total study population seems to be realistic.

Overall, 3 hypotheses will be tested (cf. section 11). The problem of multiple comparisons is addressed by using Bonferroni-Holm correction to maintain the overall error rate by testing each individual hypothesis at a statistical significance level of 1/3 times what it would be if only one hypothesis were tested (i.e., the individual tests will be based on an α level of 0.0167 instead of 0.05).

Power calculations based on the incidences given above showed that approximately 84,000 women-years would be needed to show non-inferiority of DNG versus other endometriosis medications for anemia. The calculations for anemia are based on the assumptions given in Table 2. In essence, the study is powered to exclude a two-fold risk of anemia for the DNG with at least 10% of the total exposure – if the true risk of anemia is not different for the relevant sub-cohorts.

Table 2: Power calculation^[15] for anemia based on the assumption that the true incidence of DNG cohort is not different from other endometriosis medications (reference cohort)

Test significance level, α (one-sided)	0.0083 (= 0.0167 two-sided)
Anemia Incidence for reference cohort	0.01
Non-inferiority margin	0.01 (equal to the anemia incidence for the reference cohort)
Expected anemia incidence for DNG cohort	0.01
Power (%)	90
Proportion of DNG users (% of study population)	10
Proportion of reference users (% of study population)	5

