 ${\bf 9}$  According Study Protocol, Amendment of September 30, 2017

Supporting document SOP BMT 01.09 – Doc 5002.02 – Effective date 21.03.2017

shows other incidence rates at a later point in time, a re-calculation may be necessary and will be discussed with the Safety Monitoring and Advisory Council if required.

Based on the natural history of endometriosis treatment, we anticipate that the majority of women will stop or change treatment regimen during the course of this study. We expect an incidence rate of women ceasing or changing treatment ('treatment failure') for other endometriosis medications due to lack of efficacy, loss of efficacy or an adverse drug reaction of at least 0.3. For the DNG cohort, a proportion of 0.25 of the total study population seems to be realistic.

Overall, 3 hypotheses will be tested (cf. section 11). The problem of multiple comparisons is addressed by using Bonferroni-Holm correction to maintain the overall error rate by testing each individual hypothesis at a statistical significance level of 1/3 times what it would be if only one hypothesis were tested (i.e., the individual tests will be based on an  $\alpha$  level of 0.0167 instead of 0.05).

Power calculations based on the incidences given above showed that approximately 84,000 womenyears would be needed to show non-inferiority of DNG versus other endometriosis medications for anemia. The calculations for anemia are based on the assumptions given in Table 2. In essence, the study is powered to exclude a two-fold risk of anemia for the DNG with at least 10% of the total exposure – if the true risk of anemia is not different for the relevant sub-cohorts.

**Table 2:** Power calculation [6] for anemia based on the assumption that the true incidence of DNG cohort is not different from other endometriosis medications (reference cohort)

Test significance level, α (one-sided)	0.0083 (= 0.0167 two-sided)
Anemia Incidence for reference cohort	0.01
Non-inferiority margin	0.01 (equal to the anemia incidence for the reference cohort)
Expected anemia incidence for DNG cohort	0.01
Power (%)	90
Proportion of DNG users (% of study population)	10
Proportion of reference users (% of study population)	5
Required women-years in DNG cohort	8,400
Required women-years in reference cohort	4,200
Total women years	84,000

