### 5.2 Hypothesis

Based on available data and pharmacological/pharmacokinetic considerations the a priori assumption is that use of DNG is not associated with an increased risk of anemia compared to approved hormonal medications used in the treatment of endometriosis ("endometriosis medications"). It is probable that statistical comparisons of DNG vs. other endometriosis medications will not show a difference. Therefore, a non-inferiority design to investigate the anemia risk of DNG had been chosen. The analysis will be based on the comparison of the upper confidence limit for the point estimate of the anemia hazard ratio with the predefined non-inferiority margin (cf. section 4).

 $H_0$  and  $H_A$  denote the null and alternative hypotheses, respectively.  $HR_{Anemia}$  is defined as the hazard ratio for anemia for DNG vs. OAED.

$$H_0: HR_{Anemia} \geq 2$$

$$H_A$$
:  $HR_{Anemia} < 2$ 

For clinically relevant depression (first episode or worsening), the a priori assumption is that no approved treatment for endometriosis is associated with a higher risk of depression compared with untreated endometriosis. A non-inferiority design has been chosen, with primary analysis based on the comparison of the upper confidence limit for the point estimate of the depression hazard ratio with the predefined non-inferiority limit (cf. section 4).  $HR_{Depression}$  is defined as the hazard ratio for depression (newly diagnosed or worsening) for DNG vs. OAED

$$H_0: HR_{Depression} \geq 2$$

$$H_A: HR_{Depression} < 2$$

Supporting document SOP BMT 01.09 – Doc 5002.02 – Effective date 21.03.2017

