#### 5.4.1 Incidence measures

The *incidence rate* (IR) measures the occurrence of new cases per unit of person-time.

$$IR = \frac{Number\ of\ new\ cases}{Total\ follow - up\ time}$$

The incidence rate takes into consideration the patient-specific follow-up time and it assumes a constant hazard rate. For each of n subjects the time  $t_k (k=1,...,K)$  to: (1) the end of the risk period, if recurrent events are allowed or (2) to the first occurrence of a certain event is observed. If the event was not experienced, the (censored) time to the end of the risk period is observed.

In the present study, women-years are conducted as a unit of person-time. Incidence rates are shown per 10^4 women-years (WY) unless otherwise specified.

The *incidence rate ratio* (IRR) is the proportion of two incidence rate estimates.

$$IRR = \frac{Incidence\ rate\ of\ treatment\ group}{Incidence\ rate\ of\ control\ group}$$

Supporting document SOP BMT 01.09 – Doc 5002.02 – Effective date 21.03.2017

The incidence rate ratio gives a measure of how much more likely an event occurs in subjects under exposure (treatment group) than in subjects who were not exposed (control group).

The *incidence proportion* (IP) measures the occurrence of new cases in relation to the size of the population at risk within a given period of time (cumulative incidence).

$$IP = \frac{Number\ of\ new\ cases}{Size\ of\ population\ at\ risk}$$

Exact 95% confidence intervals for prevalence, incidence proportion, incidence rate, and incidence rate ratio will be calculated in accordance with Clopper and Pearson[9].

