### Section D Comparisons and Inferential Statistics of Primary Outcomes

#### Section D-1 New anemia and reoccurrence of anemia

Table D-1.1.1 Incidence rate ratio of new anemia and reoccurrence of anemia between EMT user cohorts, AT population

Comparison	Cohort	No. of	WY	Incidence	Incidence Rate Ratio
Group		events		rate*	(95% CI)
	DNG	xx	xxxxx	x.xxxx	x.xxxx
1	OAED	xx	xxxxx	x.xxxx	(x.xxxx - x.xxxx)
2	DNG NAED	xx xx	xxxxx	x.xxxx x.xxxx	x.xxxx (x.xxxx - x.xxxx)
2	DNG	xx	xxxxx	x.xxxx	x.xxxx
3	Ex-use	XX	xxxxx	x.xxxx	(x.xxxx - x.xxxx)

Note: \*Incidence rate per 10^4 women years

Supporting document SOP BMT 01.09 – Doc 5002.02 – Effective date 21.03.2017

Table D-1.1.2 Risk of new anemia and reoccurrence of anemia obtained from Cox model (HR), AT population

Cohort	No. of	No. of WYs		Hazard Ratio (95% CI)		
	events			Crude HR	Adjusted HR	
DNG	xx	xxxxx	x.xxxx	x.xxxx	x.xxxx	
OAED	XX	xxxxx	x.xxxx	(x.xxxx - x.xxxx)	(x.xxxx - x.xxxx)	
DNG	xx	xxxxx	x xxxx	x xxxx	X.XXXX	
NAED	xx	xxxxx	x.xxxx	(x.xxxx - x.xxxx)	(x.xxxx - x.xxxx)	
DNG	VV		V VVVV	V VVVV	V	
Ex-use	xx xx	XXXXX	x.xxxx x.xxxx	x.xxxx (x.xxxx - x.xxxx)	x.xxxx (x.xxxx - x.xxxx)	
	DNG OAED  DNG NAED	DNG XX DNG XX DNG XX DNG XX NAED XX	DNG XX XXXXX  DNG XX XXXXX  DNG XX XXXXX  DNG XX XXXXX  DNG XX XXXXX	DNG XX XXXXX X.XXXX OAED XX XXXXX X.XXXX  DNG XX XXXXX X.XXXX  NAED XX XXXXX X.XXXX  DNG XX XXXXX X.XXXX	DNG     XX     XXXXXX     XXXXXX     XXXXXX       OAED     XX     XXXXXX     XXXXXX     XXXXXX       DNG     XX     XXXXXX     XXXXXX     XXXXXX       NAED     XX     XXXXXX     XXXXXX     XXXXXX       DNG     XX     XXXXXX     XXXXXX     XXXXXX	

Note: \*Adjusted for age, history of bleeding and history of anemia.

Section D-2	New depression or deterioration of existing depression
	Incidence rate ratio of new depression or deterioration of existing depression between EMT user cohorts, AT population Risk of new depression or deterioration of existing depression obtained from the Cox model (HR), AT population
Section D-3	Treatment failure
Section D-3.1	Incidence rate ratio of treatment failure between EMT user cohorts, AT population
Section D-3.2	Risk of treatment failure obtained from the Cox model (HR), AT population

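### The non-inferiority tests for anemia and depression are set and sized at 0.0083 one-sided, but the only hazard ratio limits the SAP specifies for them are 95% limits (0.025 one-sided)

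*SAP*

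**What the plan says.** **Test level.** Protocol 12 and SAP 4 count three hypotheses and state that "the individual tests will be based on an α level of 0.0167 instead of 0.05". Multiplicity "is addressed by using Bonferroni-Holm correction to maintain the overall error rate by testing each individual hypothesis" at one third of the level that a single hypothesis would have. Tables 2 and 3 give the level for anemia and depression as "0.0083 (= 0.0167 two-sided".

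**Decision rule.** For anemia, SAP 5.2 states: "The analysis will be based on the comparison of the upper confidence limit for the point estimate of the anemia hazard ratio" with the margin, which is 2. For depression it has the "primary analysis based on the comparison of the upper confidence limit for the point estimate of the depression hazard ratio" with the same margin. Both sentences refer to SAP 4 for the margin. Neither names a confidence level, and Protocol 11 names none either.

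**Intervals specified.** Under SAP 5.4.2.1, crude and adjusted HRs "will be calculated for all primary outcomes and 95% HR confidence limits (Wald) are provided". Mock Table D-1.1.2 heads its columns "Hazard Ratio (95% CI" for DNG against OAED, NAED and Ex-use alike. SAP 5.4.1 uses the same level for the incidence measures: "Exact 95% confidence intervals for prevalence, incidence proportion, incidence rate, and incidence rate ratio will be calculated". Neither document mentions a 98.33% interval, an adjusted p-value or an order of testing.

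**The concern.** A rule based on an upper confidence limit is a test, and its error rate is set by the confidence level. The power section fixes one level, while the analysis section and the table shells print another. A programmer who follows SAP 5.4.2.1 and Section D would have only a 95% upper limit to compare with 2. A statistician who starts from SAP 4 would use 98.33%.

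At stake are two of the three primary outcomes, on which the study's safety conclusions rest. For some results the two limits give opposite answers. The name Bonferroni-Holm does not settle the matter. Holm uses a different level at each step, and the text gives one level for every test.

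**Working it through.** **Inputs** (Protocol 12 and SAP 4, Tables 2 and 3; identical for anemia and depression): incidence 0.01 per woman-year (WY) in both cohorts, margin HR 2, one-sided alpha 0.0083 (0.05/6), power 90%, 8,400 WY on DNG and 4,200 WY on reference (2:1), DNG 10% of total exposure, 84,000 WY in total. Planned events are therefore 84 and 42, or 126.

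**1. Reproduce the plan's figure.** Schoenfeld's formula with 2:1 allocation is

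events = (z(1−alpha) + z(0.90))² / [(2/9) × (ln 2)²].

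- One-sided 0.05/6: z = 2.394, so events = (2.394 + 1.2816)² / (0.2222 × 0.4805) = 126.5. At 0.01 per WY that is 12,653 WY. Two thirds (8,435) are on DNG, and dividing by 10% gives 84,355 WY. The plan states 8,400 and 84,000, so it reproduces.
- One-sided 0.025: z = 1.960, events = 98.4, total 65,609 WY. This does not reproduce.

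The study was therefore sized for the stricter limit. SAP 3 adds a year of follow-up in order to reach 84,000 WY.

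**2. Match levels to intervals.** One-sided 0.0083 is the upper limit of a two-sided 1 − 2 × 0.05/6 = 98.33% interval. A 95% interval is one-sided 0.025, three times that level.

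**3. What each limit does at the planned events.** SE of log HR = √(1/84 + 1/42) = 0.189. The largest passing estimate is 2 × exp(−z × SE). Power at a true HR of 1 is Φ(ln 2/SE − z).

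| Deciding limit | z | Largest passing HR | Power at HR 1 | Nominal error at HR 2 |
|---|---|---|---|---|
| 98.33% | 2.394 | 1.27 | 90% | 0.83% |
| 95% | 1.960 | 1.38 | 96% | 2.5% |

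An estimate between 1.27 and 1.38 fails by the first limit and passes by the second.

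**4. Exact check of the error.** The event counts are taken as Poisson at the planned WY with a true HR of 2 (means 168 and 42), with a Wald limit on the log rate ratio. The probability of declaring non-inferiority is 1.0% with the 98.33% limit and 2.7% with the 95% limit.

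**5. Holm.** With three hypotheses the step levels are one third, one half and all of the overall level. If the overall level were 0.025 one-sided (an assumption), the steps would be 0.0083, 0.0125 and 0.025. A 95% limit would then be right only for a hypothesis reached last, after the other two are rejected. It could not be the default for both safety outcomes.

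**6. Secondary: Table 4.** The treatment-failure table labels 0.0167 as one-sided, while Tables 2 and 3 treat 0.0167 as two-sided. Take 0.25 and 0.30 as proportions (an assumption), with 2,950 and 1,475 as group sizes. The SE of the difference is then √(0.25 × 0.75/2,950 + 0.30 × 0.70/1,475) = 0.01435. Power is Φ(0.05/0.01435 − z): 91% at 0.0167 one-sided and 86% at 0.0083. If they are rates per WY, the corresponding ranges are 79–82% and 71–74%, depending on the test.

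**The case against.** The strongest reply is that the SAP already gives the level. Section 4 belongs to the same document, fixes 0.0167 per test and prints the one-sided equivalent, so a 98.33% interval follows. SAP 5.4.2.1 also reads like a reporting rule. The same 95% format serves the comparisons with NAED and Ex-use, which carry no non-inferiority hypothesis, and 95% is the display level for the incidence measures. No sentence says that the 95% limit decides.

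This stands in part. A reader might infer that no decision limit exists at all; that goes too far, because SAP 4 implies one. The 2.5% error is conditional on the 95% limits being used to decide, and is not a planned rate. But the implied interval is never specified or tabulated, the one that is specified contradicts it, and the reference from 5.2 to SAP 4 concerns the margin.

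Two other inferences are not supported. One is that all three tests together were to be held to 2.5% one-sided. Neither document says so, and with Table 4 as labelled the listed one-sided levels sum to 0.0083 + 0.0083 + 0.0167 = 0.0333. The other is that a thin reference cohort makes the stricter limit unaffordable. SAP 3.1 (footnote 8) reports an OAED shortfall, but also a recommendation to restart recruitment for 2,000 OAED patients. SAP 3.2 shows a second recruitment period, and neither section gives an event count.

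**Conclusion.** The concern holds as an inconsistency between the stated test level and the specified interval. Deciding on the limits that the SAP specifies would triple the nominal error per outcome, from 0.83% to 2.5% (exact check: 1.0% to 2.7%). It would also raise the largest passing HR from 1.27 to 1.38. Deciding on the limit that the test level implies gives the 90% power that was planned; the 96% was never the design value.

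The sizes rest on the planning scenario of 84 and 42 events at 0.01 per WY, and on independent events. SAP 5.4.2.1 includes recurrent events and adjusted models, so the actual figures will differ. The threefold ratio of the nominal levels does not depend on the event counts. The Table 4 label is a smaller, separate inconsistency.

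**What to change.** - In SAP 5.2, 5.4.2.1 and mock Section D, name the upper limit of the two-sided 98.33% interval for DNG versus OAED as the limit compared with 2 for anemia and depression. State whether it belongs to the crude or the adjusted HR, since both are tabulated.
- Alternatively, if Holm is intended, state the overall one-sided level first, then write out the steps and the interval that matches each. If it is not intended, call the rule Bonferroni.
- Keep the 95% limits and label them descriptive.
- In Table 4, use the same one-sided or two-sided convention as Tables 2 and 3. Restate the power at the level actually used, and say whether 0.25 and 0.30 are proportions or rates.

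The cost is wording in three places, the Table 4 correction and a confidence-level option in the program. No new data are needed. Relative to deciding on 95% limits, power in the planning scenario is 90% instead of 96%. The change should be made before the final analysis.

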1. INTRODUCTION

Endometriosis is a common, chronic, gynecological disease characterized by pain and impaired fertility. Prevalence estimates vary widely, however, the proportion of premenopausal women living with endometriosis is thought to be approximately 10% [1]. Endometriosis causes chronic inflammation, ovarian cyst formation, fibrosis and adhesions [1]. There seems to be little correlation between the extent of the disease and severity of pain experienced [2]. However, symptoms seem to respond to decreased circulating estrogen [3] and the mainstay of medical treatment is hormonal induced anovulation and a reduction in endogenous estrogen production.

While currently approved medications for endometriosis have proven to be effective in decreasing pelvic pain, many have clinically relevant side-effects. Danazol, a testosterone analogue, can cause androgenization and GnRH agonists are known to decrease bone mineral density. Consequently, treatment for endometriosis with these medications needs to be stopped after 6-12 months. Post-treatment endometrial lesions tend to regenerate, with many women's symptoms reoccurring 1-2 months after the cessation of treatment. Some countries in Europe also allow the use of progestogens for the treatment of endometriosis, however, there is currently no pharmaceutical preparation licensed for the treatment of endometriosis in all member states of the European Union.³

Dienogest (DNG) is a 19-nortestosterone derivative progestogen that is highly selective for progesterone receptors [4]. DNG has been available as part of a low-dose combined oral contraceptive containing 2mg of dienogest and 30µg of ethinylestradiol (DNG/EE) in Germany since 1995. As a progestin in DNG/EE, DNG is known for having strong endometrial effects that improve dysmenorrhoea and decrease the duration of menstrual bleeding [5]. In addition, progestogens may also modulate pain associated with endometriosis by dampening neuronal activity [3]. As a monotherapy for the treatment of endometriosis DNG 2mg/day has been available in Japan since 2008. In Japan it has been found to be a reliable and effective treatment for dysmenorrhea, premenstrual pain, dyspareunia and diffuse pelvic pain associated with endometriosis associated pelvic pain with improved tolerability compared with 3.75mg leuprolide acetate (LA) [7-8]. Unlike LA, DNG has minimal effects on bone density and may offer women a new option for the long-term control of endometriosis symptoms.

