#### 5.1 Analysis sets

There are no specific inclusion or exclusion criteria. However, women with a language barrier, a non-hormonal or not newly prescribed baseline medication or women who are pregnant at study enrollment will be excluded from the analysis. The final analyses will include both an "as treated" (AT) and an "intention-to-treat" (ITT) analysis. All women who are not excluded from the analysis will be assigned to the ITT and AT population at baseline. Only women with follow up information will be considered for longitudinal analysis (e.g. distribution of outcomes over time, incidence rates, regression). Women who never started their prescribed baseline medication will be considered in the ITT analysis, but excluded from the AT analysis. The safety conclusions of the study will be based on the AT analysis.

Supporting document SOP BMT 01.09 – Doc 5002.02 – Effective date 21.03.2017

This study follows three cohorts: users of Visanne (DNG), users of other medication approved for the treatment of endometriosis (OAED) and users of non-approved hormonal medications prescribed for endometriosis treatment or those approved only in some participating countries (NAED).

Distribution of women, population characteristics (baseline and follow up) as well as clinical outcomes will be presented for the following cohorts and sub-categories.

Cohort Sub-category for presentation	
DNG	Complete cohort
OAED	GnRH-a, Danazol, complete cohort
NAED	Combined hormonal contraceptives, other progestins, complete

The cohorts consist of new users (starter and restarter) or switcher of a hormonal endometriosis treatment. For the primary analysis, outcomes of interest or adverse events will be assigned to the treatment at the time the outcome or the event occurred. Women with multiple exposure or unspecific treatment will be specified as "Allocation unknown". Women who stopped their treatment will be assigned to an "Ex-use" cohort.

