#### 5.4.2 Regression models

Regression analysis will be performed if a sufficient number of confirmed events are available for estimation, i.e. n≥5 confirmed events in each of the comparison groups.

Potential confounders such as

- age, personal and family history of depression, history of anemia, history of bleeding disorders and severity of pain will be included as time-invariant cofactors.
- EMT user type at follow up, use of Antidepressants/SSRI and current or worsening depression (primary outcome) will be included as time-dependent cofactors.

For each primary outcome, a summary table with predefined potential prognostic factors and the corresponding relative risk estimators is provided.

The final decision on the confounding variables will be made by the Safety Monitoring and Advisory Council:

Primary outcome variable	Predefined Prognostic Factors 	
Anemia	Age, history of anemia, history of bleeding disorders	
Depression	Age, family and personal history of depression, use of Antidepressants/SSRI	
Treatment Failure	Age, family and personal history of depression, severity of pain	

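### The Cox model counts repeat events in the same woman, but the SAP names no variance that allows for them, so the upper limit that decides non-inferiority may be too low

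*SAP*

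**What the plan says.** SAP 5.4.2.1 says of the primary-outcome models "In the Cox model, recurrent events are included" and "95% HR confidence limits (Wald) are provided". SAP 5.4.1 shows what recurrent means: follow-up runs to "the end of the risk period, if recurrent events are allowed or (2) to the first occurrence of a certain event is observed". That contrast makes sense only for more than one event in the same woman.

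The interval carries the decision. SAP 5.2 rests anemia non-inferiority on the "comparison of the upper confidence limit for the point estimate of the anemia hazard ratio with the predefined non-inferiority margin", with a margin of 2, and treats depression the same way. SAP 5.1 allocates as treated: "outcomes of interest or adverse events will be assigned to the treatment at the time the outcome or the event occurred". Regression needs only "n≥5 confirmed events in each of the comparison groups" (SAP 5.4.2). For incidence rate ratios, SAP 5.4.1 says: "Exact 95% confidence intervals for prevalence, incidence proportion, incidence rate, and incidence rate ratio will be calculated in accordance with Clopper and Pearson".

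On what counts as an event, SAP 4 bases its anemia rate on new and recurrent cases together, and the titles of Tables C-1.1.2 to C-1.1.13 and Section D-1 include reoccurrence. In mock Table C-3.9.1 (numbered C-4.2.1 in the list of tables), *Recurrent anemia* is the first row of the breakdown that follows *Not confirmed*. Table C-3.10.1 has a matching row for depression. Neither label is defined.

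**The concern.** Wald describes the form of an interval (estimate plus or minus a multiple of a standard error), not where the standard error comes from. Two analysts could follow 5.4.2.1 faithfully, one with model-based errors and one with errors clustered on the woman, and report different upper limits. A woman who has had one anemia or depressive episode may well be more prone to another. Model-based errors treat her episodes as independent, overstate the information and usually give a limit that is too low. In a non-inferiority comparison, that favors declaring a doubling of risk excluded.

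The table row raises a second question: whether an on-study anemia recurrence counts at all. Different answers in different tables would leave the content of the primary analysis unclear.

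**Working it through.** **1. The plan's own figure.** Inputs from SAP 4, Table 2: one-sided alpha 0.0083, power 90%, margin 2, 8,400 and 4,200 WY (2:1), rate 0.01. The Schoenfeld formula gives (2.394 + 1.282)² / [(2/9)(ln 2)²] = 126.5 events. The plan's 12,600 WY × 0.01 = 126 events (84 vs 42), so its figure reproduces. The formula treats events as independent.

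**2. Inflation from repeats.** The documents give no recurrence share, so four mixes of women with 1/2/3 events among affected women are assumed. For a clustered arm the variance factor is E[N²]/E[N] − m. N is the number of events in an affected woman and m is the mean count over all women in the arm. Subtracting m matters because independent events also produce some women with two events. With 84,000/25,000 = 3.36 WY per woman (assumed), m = 0.02 × 3.36 = 0.0672 for DNG at a true ratio of 2, and 0.01 × 3.36 = 0.0336 for the reference cohort. Chance alone would then give repeats in 3.3% and 1.7% of affected women.

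**3. Error at a true ratio of 2.** Expected events are 168 vs 42. Write f = E[N²]/E[N], g1 = f − 0.0672 and g0 = f − 0.0336. The variance ratio is (g1 + 4)/5 if only DNG is clustered and (g1 + 4·g0)/5 if both arms are. Error = Φ(−2.394/√ratio).

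| Mix, % | E[N] | E[N²] | f | Ratio, DNG only | Error | Ratio, both | Error |
|---|---|---|---|---|---|---|---|
| 95/5/0 | 1.05 | 1.15 | 1.095 | 1.006 | 0.0085 | 1.055 | 0.0099 |
| 90/8/2 | 1.12 | 1.40 | 1.250 | 1.037 | 0.0094 | 1.210 | 0.0148 |
| 80/15/5 | 1.25 | 1.85 | 1.480 | 1.083 | 0.0107 | 1.440 | 0.0230 |
| 70/20/10 | 1.40 | 2.40 | 1.714 | 1.129 | 0.0121 | 1.674 | 0.0321 |

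With the stated 95% limits (one-sided 0.025, so 1.96 in place of 2.394), the same ratios give 0.0253 to 0.0326 and 0.0282 to 0.0649. On-treatment time per woman may be below 3.36 WY, which shrinks m. With m = 0 the 0.0083 ranges become 0.0089 to 0.0126 and 0.0111 to 0.0337.

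**4. Repeats in the other arm.** As-treated allocation lets one woman contribute to both arms, and her contributions then partly cancel in the log ratio. With the woman-level variance Σ(A1/D1 − A0/D0)², where A1 and A0 are her events under DNG and reference and D1 and D0 the arm totals, both arms clustered and no mean subtraction, the error is about 0.010 to 0.017 if 25% of repeats fall in the other arm. It stays at about 0.008 if 50% do.

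**5. Does clustering on the woman repair it?** A 400,000-run compound-Poisson simulation gave 10%, 20% or 30% of cases in both arms exactly two events, without the mean subtraction. Model-based errors gave 0.0158, 0.0213 and 0.0276; a per-woman variance gave 0.0092 to 0.0100, against 0.0095 with no repeats. At small counts it helps less. With about 5 expected reference events, the clustered error is 0.019 to 0.022, much as with no recurrence; with about 10 it is 0.010 to 0.011.

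**6. The table row.** The other rows in that breakdown of C-3.9.1 are reasons for non-confirmation, and a repeat report or pre-study event has its own row. Neither SAP 5.4.3 nor Protocol Appendix 1 makes recurrence a ground for non-confirmation. Read at face value, the row conflicts with the titles of C-1.1.2 and D-1.

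**The case against.** The SAP is silent rather than wrong: a sandwich variance also yields Wald limits, and no sentence prescribes model-based errors. A reader might infer that the plan specifies an invalid analysis; the text does not say that. But because the limit is the decision rule, a choice left open until the data are seen is still a gap.

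The size is assumption. A reader might take the top of the range as the expected error, but that needs 30% of affected women in both arms to have repeats. Protocol 1 says of danazol and GnRH agonists that "treatment for endometriosis with these medications needs to be stopped after 6-12 months", which makes repeats mainly under DNG the more plausible case, and there the inflation is modest. Nor is the direction certain, given events in both arms. Adjustment for history of anemia would absorb some between-woman variation. That is only partial: it is a time-invariant covariate, not updated by a first on-study event, and crude ratios are reported too.

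The row belongs to a secondary self-report table, its indentation is lost in the text, and it might mean recurrent reports that fail 5.4.3, which would remove the conflict. A reader might infer that cases will be misclassified. The documents do not support that: confirmation follows SAP 5.4.3 and blinded adjudication (Protocol 8 and Appendix 2). *Recurrent depression* may be a deliberate exclusion from the new-or-worsening endpoint.

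**Conclusion.** The gap is real and worth closing; its size is unknown. If model-based errors are used and repeats cluster within women, the upper limit is probably too low. A nominal 0.0083 becomes about 0.0085 to 0.012 with repeats only under DNG, or 0.010 to 0.032 with both arms clustered. This rests on the assumed 5% to 30% recurrence share and 3.36 WY per woman. If repeats are rare, or about half fall in the other arm, there is little or no inflation.

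The two parts are partly alternatives. If anemia recurrences count, the variance needs stating and the C-3.9.1 row needs correcting or defining. If they are excluded as not confirmed, few anemia repeats reach the Cox model, the variance issue for anemia largely disappears, and it is the reoccurrence titles and the 5.4.2.1 sentence that are wrong.

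**What to change.** In SAP 5.4.2.1, state that Wald limits in every Cox model with recurrent events use a robust sandwich variance clustered on the woman, with a caution when events are near the minimum of 5 per group. Add a Cox model for time to first confirmed event as a sensitivity analysis for anemia and for depression.

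Define *Recurrent anemia* and *Recurrent depression* in C-3.9.1 and C-3.10.1. Reconcile the anemia row with C-1.1.2 and D-1, so that an on-study recurrence meeting 5.4.3 is counted the same way in every table. If recurrences are meant to be excluded, correct the titles and the 5.4.2.1 sentence instead. For depression, state how the row relates to the existing endpoint without changing that endpoint. Labeling the rate-ratio limits as descriptive where repeats are counted is optional.

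The cost is SAP wording, a woman identifier with a clustering option in the programs, and one extra table for each of the two outcomes. Intervals widen if repeats are common. At 84 vs 42 events and a ratio of 1, the standard error is √(1/84 + 1/42) = 0.189, the one-sided 0.0083 upper limit is exp(2.394 × 0.189) = 1.57, and power is Φ(0.693/0.189 − 2.394) = 90%. At a ratio of 1, m = 0.0336 in both arms. With only DNG clustered, the variance ratio (f − 0.0336 + 2)/3 runs from 1.021 to 1.227, giving limits of 1.58 to 1.65 and power of 89% to 82%. With both arms clustered, f − 0.0336 runs from 1.062 to 1.681, giving limits of 1.59 to 1.80 and power of 88% to 67%. The first-event model leaves out 1 − 1/E[N] = 5% to 29% of events in a clustered arm, so it answers a narrower question and should stay a sensitivity analysis.
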